		W2	W4	W8	W16	W24	W32	W40	EoTP/W48	EoTP + 8 weeks	EDV ^c	UNS ^d		
Study week(s)		Visit window	±2 d	±2 d	±7 d	±7 d	±3 d							
QoL questionnaires (EQ-5D-5L, DLQI, ABQoL)	X					X				X		X		Section 8.2.2

ABQoL=Autoimmune Bullous Disease Quality of Life; AE=adverse event; BP=bullous pemphigoid; BPDAI=Bullous Pemphigoid Disease Area Index; CDA=control of disease activity; DLQI=Dermatology Life Quality Index; ECG=electrocardiogram; eCRF=electronic case report form; EDV=early discontinuation visit; efgartigimod PH20 SC=efgartigimod for SC administration coformulated with rHuPH20; EoTP=end-of-treatment period (visit); GTI=Glucocorticoid Toxicity Index; GTI-AIS=GTI Aggregate Improvement Score; GTI-CWS=GTI Cumulative Worsening Score; GTI-SL=GTI Specific List; IGA-BP=Investigator Global Assessment of Bullous Pemphigoid; ██████████ IMP=investigational medicinal product; NA=not applicable; NRS=numerical rating scale; PBMC=peripheral blood mononuclear cell; PD=pharmacodynamics; PK=pharmacokinetics; QoL=quality of life; rHuPH20=recombinant human hyaluronidase PH20; SC=subcutaneous; SoA=schedule of activities; UNS=unscheduled visit; W=week

Note: Assessments indicated in gray font will only be recorded on the ARGX-113-2009 eCRF and not on the ARGX-113-2010 eCRF.

- ^a Participants for whom IMP was temporarily interrupted at the time of the EoTP in ARGX-113-2009 must follow the SoA in Table 1 until the investigator has determined that it is safe for the participant to receive treatment. If the participant requires treatment with efgartigimod PH20 SC, they must follow the SoA in Table 2 as of day X (refer to Section 5.5).
- ^b Participants who have not received efgartigimod PH 20 SC since baseline must follow the SoA in Table 1 until the investigator decides that efgartigimod PH20 SC should be initiated. If relapse occurs during the study, efgartigimod PH20 SC must be initiated. Participants who initiate efgartigimod PH20 SC must follow the SoA in Table 2 as of day X (refer to Section 6.3 for more details).
- ^c When a participant is withdrawn from the study (for any reason listed in Section 7.2), study sites should make every effort to schedule the EDV within 7 days after the last contact with the participant and a safety follow-up visit 8 weeks after the previous contact.

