1.1 STUDY OBJECTIVES AND ENDPOINTS

Table 1: Objectives and endpoints

Objectives	Endpoints
Primary	
To assess the long-term safety and tolerability of treatment with efgartigimod PH20 SC in participants with BP	
 • Incidence and severity of treatment-emergent AEs, SAEs, and AESIs • Rate of treatment discontinuation because of safety concerns
Secondary	
To assess the long-term efficacy and durability of response with efgartigimod PH20 SC treatment in participants with BP	
 • Proportions of participants achieving^a: 
 ○ CR while off OCS for ≥ 8 weeks ○ CR or PR while off OCS for ≥ 8 weeks ○ CR while on minimal OCS therapy for ≥ 8 weeks. (Minimal OCS therapy is defined as ≤ 0.10 mg/kg/day of prednisone [or an equivalent dose of another OCS]) ○ CR while off both OCS and efgartigimod PH20 SC for ≥ 8 weeks^b ○ CR or PR while off both OCS and efgartigimod PH20 SC for ≥ 8 weeks^b • Duration of sustained remission • Proportion of participants who relapse • Time to relapse • Incidence and severity of relapse • BPDAI activity scores, IGA-BP scores, and itch NRS over time • Rate of treatment failure

	Statistical Analysis Plan	
ARGX-113-2010	Final analysis	Final 1.0 of 29APR2025

Additional secondary	
To evaluate the impact of efgartigimod PH20 SC treatment in reducing long-term glucocorticoid-associated toxicity in participants with BP	
 GTI-related scores, including the GTI-AIS, GTI-CWS, and GTI-SL over time
To evaluate the impact of efgartigimod PH20 SC treatment on QoL in participants with BP	
 EQ-5D-5L, DLQI, and ABQOL scores over time
To evaluate the PD and immunogenicity of efgartigimod PH20 SC in participants with BP	
 Percent change from baseline over time for anti-BP180 and anti-BP230 antibody levels Incidence and prevalence of ADA against efgartigimod (serum levels)
Exploratory	
[REDACTED]	
 [REDACTED]

- ^a These endpoint criteria can only be met when participants are off rescue therapy.
- ^b The endpoint applies only to participants who have stopped receiving efgartigimod PH20 SC before protocol amendment 2 is effective.

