1.3 STATISTICAL HYPOTHESIS

No formal hypothesis testing will be conducted in this open-label study.

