1.4 EXPECTED SAMPLE SIZE

The maximum number of participants in this study is the number of participants who complete the week 36/EoTP visit in ARGX-113-2009 and meet the eligibility criteria to roll over to this study.

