2. GENERAL METHODOLOGY

2.1 ANALYSIS SETS

2.1.1 *Analysis sets*

The following participant analysis sets (PAS) will be used:

Rollover (ROL) analysis set: All participants who rolled over from ARGX-113-2009 and provided informed consent for participation in ARGX-113-2010

Safety (SAF) analysis set: All participants from the ROL analysis set who received at least one dose of IMP

Notes:

- Provided informed consent is defined as having a complete informed consent signature date in the database.
- Received at least one dose of IMP is defined as having an exposure date or any information confirming exposure present in the database.

2.1.2 *As planned versus as actual analysis*

Not applicable. All endpoints will be analyzed for the total group of participants, regardless of previous treatment in ARGX-113-2009 (placebo or efgartigimod PH20 SC).

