Adverse events will be allocated to phases as described in section 5.1.2. Concomitant therapies and procedures will be allocated to phases and (sub)periods as described in section 3.3.2. All other assessments will be allocated to phases and (sub)periods based on the assessment date/time. In case of (partially) missing date/time fields disabling allocation of an assessment to phases or (sub)periods, information from the visit label, time point label and the protocol schedule of activities will be used to allocate to the correct phase.

For efficacy assessments without time part, an assessment on the day of switch from observation phase to treatment phase will be considered as part of the treatment phase. Likewise, an assessment on the day of switch from treatment period 1 to treatment period 2 will be considered as part of treatment period 2.

2.2.2 *Baseline and change from baseline*

Study baseline is defined as the first available and nonmissing value at the baseline visit (scheduled or unscheduled) in ARGX-113-2010. This value corresponds with the value at the EoTP visit in ARGX-113-2009 (and is copied over into the database of ARGX-113-2010 at SDTM level).

Change from baseline is defined as:

- Change from baseline at time point t = value at time point t – baseline value.

Percentage change from baseline at time point t is defined as follows:

- When baseline value is not zero: $100 * ((\text{value at time point } t - \text{baseline value}) / \text{baseline value})$
- When both baseline value and value at time point t are zero: 0
- When baseline value is zero and value at time point t is not zero: not calculated

For immunogenicity assessments, the study baseline selection will be performed by sample (not by parameter) in order to keep the ADA and NAb results of a sample together. Furthermore, values resulting in an unevaluable ADA status are given the lowest priority when the selection is made.

For evaluation of PD parameters, a treatment period-specific baseline (TPnB) will be defined:

	Statistical Analysis Plan	
ARGX-113-2010	Final analysis	Final 1.0 of 29APR2025

- For a treatment period, TPnB is the last available and non-missing value prior to the first IMP administration in the treatment period. Assessments on day 1 of a treatment period without time collection or with time information exactly equal to the time of first IMP administration and which are planned predose will be considered as predose.

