- 9) Time to relapse:
 - Start date is the first day with status CDA, CR or PR in the treatment period (or observation phase)
 - End date is:
 - the start date of first relapse after having or achieving CDA, CR or PR
 - the end date of the study (end date of last phase), if no relapse
 - Time to relapse (in days) = end date - start date + 1
- 10) For participants with relapse, severity of (first) relapse will be calculated as the BPDAl total score at the onset of relapse (use the first available nonmissing BPDAl total score in the interval of relapse) minus the BPDAl total score at the preceding visit (use the most recent preceding visit for which a nonmissing BPDAl total score is available). Severity of relapse will be categorized as <0 , $0- <10$, $10- <20$, $20- <30$, or >30 .

	Statistical Analysis Plan	
ARGX-113-2010	Final analysis	Final 1.0 of 29APR2025

The following endpoints will be derived **overall**:

- 11) Changes and percent changes from study baseline will be calculated for BPDAI activity and total score.
- 12) Changes from study baseline will be calculated for itch NRS 24-hour average and worst scores.
- 13) C-GTI: Composite Glucocorticoid Toxicity Index comprises the Aggregate Improvement Score (AIS) and the Cumulative Worsening Score (CWS). Details of AIS and CWS derivations are specified in appendix 9.1.
- 14) A total ABQOL score is calculated as the sum of all 17 items score 0 to 3 with higher score indicating worse condition. Missing items are imputed with the average score of the present items if at least half (9) of the items are present. The total score is rounded to the highest integer.
- 15) Changes from study baseline will be calculated for EQ-5D-5L VAS score, DLQI score and total ABQOL score.

4.1.3 *Presentation of results*

Efficacy results will be presented for the ROL analysis set, unless mentioned otherwise. For tables by analysis visit, only the study baseline and last assessment analysis visits will be shown. Other analysis visits will be included in listings.

A frequency tabulation will be created for the number and percentage of participants who achieved CROff at least once during the study (i.e., in any treatment period). The table will also present the number of participants who are evaluable for the endpoint at least once during the study. This number will serve as denominator for the percentage calculation. This table will be based on the SAF analysis set.

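### BPDAI, IGA-BP, itch and QoL are tabulated only for all rollovers, so never-dosed participants and off-drug time are mixed into results that serve an objective about treatment; SAF companion tables should be added

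*SAP*

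**What the plan says.** The secondary efficacy objective in SAP 1.1 reads "To assess the long-term efficacy and durability of response with efgartigimod PH20 SC treatment in participants with BP". BPDAI activity, IGA-BP and itch NRS over time sit directly under it; QoL has its own objective, which also refers to the impact of efgartigimod treatment.

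SAP 2.1.1 defines ROL as "All participants who rolled over from ARGX-113-2009 and provided informed consent for participation in ARGX-113-2010" and SAF as "All participants from the ROL analysis set who received at least one dose of IMP". SAP 4.1.3 makes ROL the default for efficacy: "Efficacy results will be presented for the ROL analysis set, unless mentioned otherwise". The list of tables follows this for BPDAI, IGA-BP and itch (14.2.1.10 to 14.2.1.14) and for QoL (14.2.1.17 to 14.2.1.22).

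Under SAP 4.1.2 these endpoints are derived overall, not by treatment period. Changes in BPDAI, itch and the QoL scores are taken from study baseline, which SAP 2.2.2 equates with the end-of-treatment value of ARGX-113-2009. IGA-BP and the QoL items are frequency tables, not change scores. Only baseline and last assessment are tabulated. SAP 2.2.6 defines last assessment for these endpoints as the last nonmissing postbaseline value, with no requirement that the participant be on IMP.

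Elsewhere treated time is separated. CRoff, CR/PRoff and CRmin are derived per treatment period on SAF. Pharmacodynamics (PD) uses SAF and its own pre-dose reference: "For evaluation of PD parameters, a treatment period-specific baseline (TPnB) will be defined".

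**The concern.** A reader who wants to know how BPDAI, itch, IGA-BP or QoL behaved under efgartigimod has only one set of tables, and three kinds of untreated experience enter it.

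- **Never-dosed participants.** SAP Table 2 allows an observation phase that runs to week 48 or early discontinuation with no treatment period.
- **Pre-dose time in late starters.** Under Protocol Table 1, footnote b, "Participants who have not received efgartigimod PH 20 SC since baseline must follow the SoA in Table 1" until the investigator decides to initiate, and relapse makes initiation mandatory. For someone who starts at relapse, change is still measured from rollover.
- **Drug-free follow-up.** BPDAI, IGA-BP and itch are scheduled at the follow-up visits, so a completer's last value comes after dosing has ended.

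At stake is what the summaries mean. A participant who relapses untreated and then responds can appear as slightly worse, and a participant who stays well without drug appears as stable. The study is descriptive ("No formal hypothesis testing will be conducted in this open-label study"), so no error rate or power is affected. For these endpoints, however, the descriptive tables are the whole result.

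**Working it through.** The plan states no effect size, and its sample size is only an upper bound ("The maximum number of participants in this study is the number of participants who complete the week 36/EoTP visit in ARGX-113-2009"). There is no figure to reproduce. The check traces the definitions and then uses simple arithmetic.

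**1. Off-drug time, from the documents' own timings**
- Protocol 6.3 allows initiation until week 45. Protocol Table 2, footnote l, makes week 48 the last dosing point. Follow-up lasts 8 weeks.
- Latest starter: 45 weeks before the first dose, then weekly doses at weeks 45, 46, 47 and 48 (4 doses), then 8 weeks of follow-up. Time outside the first-to-last-dose span is 45 + 8 = 53 of 56 weeks, and 53/56 = 95%. This is the extreme case, not a typical one.
- Completer dosed to week 48: the last BPDAI, IGA-BP and itch values fall at EoTP + 8 weeks, so 8 weeks after the last dose.
- QoL is not scheduled at F1 or F2 in Protocol Table 2. Follow-up contamination therefore applies to BPDAI, IGA-BP and itch, not normally to QoL.

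**2. Mixing in never-dosed participants**

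Pooled mean = (1 - f) × T + f × U, where f is the never-dosed share, T the treated mean change and U the never-dosed mean change. None of the three is in the documents.
- Assume T = -10 and U = 0. With f = 0.05: 0.95 × (-10) = -9.5. With f = 0.25: 0.75 × (-10) = -7.5.
- Assume T = -20 and U = +10. With f = 0.05: -19.0 + 0.5 = -18.5. With f = 0.30: -14.0 + 3.0 = -11.0.
- The shift from T is f × (U - T). It is zero if both groups change alike, and it reverses sign if the never-dosed group improves more.

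**3. One late starter (assumed scores)**
- BPDAI 0 at rollover, 20 on day X, 2 at last assessment.
- From study baseline, as planned: 2 - 0 = +2.
- From the last value before first dose: 2 - 20 = -18.

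**4. Percent change in BPDAI**
- Under SAP 2.2.2 a baseline of 0 with a last value of 0 counts as 0%. A baseline of 0 with a nonzero last value is not calculated.
- Among participants clear at rollover, those who stay clear remain in the percent-change summary and those who worsen drop out.

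**5. Whether data exist for a treated-only version**
- Protocol Table 2 schedules BPDAI, IGA-BP and itch on day X, so a pre-dose value should exist for late starters.
- QoL is not scheduled on day X. A pre-dose QoL value would often be the rollover value, or an older observation-phase one.

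**The case against.** The strongest reply is that the plan does what the protocol asks. Protocol 9.3.1 fixes the rollover value as baseline, the endpoint is scores over time, and no estimand is defined. The objective also covers durability, and Protocol 4.2 wants to know whether remission lasts after stopping drug, so some off-drug time is intended content. SAP 2.4.2 labels ROL displays simply as Total and reserves the efgartigimod label for SAF. Using SAF for responses within a treatment period and ROL for the whole-study course is coherent; relapse is also on ROL. All of this stands. It is a good reason to keep the ROL tables, but not a reason to have no treated-only table.

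A reader might infer that the -18 in the example is the true drug effect and the +2 an error. The documents do not support that. The +2 correctly describes status against rollover, a score taken at a flare will tend to fall anyway, and topical or oral corticosteroids may be given alongside. The relapse endpoints, including BPDAI-based severity, also capture the flare.

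After amendment 2 all new rollovers are to receive efgartigimod (Protocol 4.1). Never-dosed participants should therefore come mainly from earlier entrants, with some from interruptions at rollover (Protocol 5.5) or decisions not to initiate (Protocol 7.1.1). That limits the likely share without giving it.

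The individual scores are listed, so a treated-only result could be rebuilt by hand. That helps a later analyst more than a reader of the report.

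**Conclusion.** The point holds as a gap in presentation. For BPDAI, IGA-BP, itch and QoL, the only tabulated results mix never-dosed participants and pre-dose observation time with treated time; for the first three they also mix in drug-free follow-up. Nothing planned isolates the treated result that the objective asks about, although the SAP makes that separation for the remission endpoints and for PD.

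A reader might go further and infer that the ROL summaries materially dilute or misreport efficacy, or that they should be replaced. The documents do not support this. The never-dosed count is not given, so neither size nor direction can be established, and the range of -9.5 to -7.5 rests wholly on the assumed 5% to 25%, -10 and 0. The ROL tables follow the protocol's baseline and carry durability information that SAF would drop.

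This is a low-cost improvement that should be made, not an error that invalidates the plan.

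**What to change.** Keep the ROL tables against study baseline and add SAF companions.

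- **BPDAI and itch:** change from the last value before the first IMP dose (TP1B, which for those dosed at rollover is the study baseline) to the last on-IMP value.
- **IGA-BP:** frequencies at those same two time points.
- **QoL:** restrict to SAF but keep study baseline, because no day X assessment is scheduled.
- **Layout:** show participants dosed at rollover separately from later starters, with a footnote that a TP1B taken at relapse is open to regression to the mean and to concurrent oral or topical corticosteroids.

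Three definitions need a sentence each. First, say that a day X score without a recorded time counts as pre-dose; SAP 2.2.1 otherwise places efficacy assessments on the switch day in the treatment phase. Second, define the last on-IMP value from the On IMP subperiod; the PD last-assessment rule cannot be copied because it admits follow-up values. Third, for participants with two treatment periods, say which period supplies the value; taking it from period 1 pairs it with TP1B.

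The cost is at most 11 companion tables (5 for BPDAI, IGA-BP and itch, 6 for QoL) on existing shells. No new data are needed. TP1B is already specified as an analysis visit in SAP Table 3. SAF plus TP1B without the on-IMP endpoint would not be enough, since the last value would still fall in follow-up.

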3. OBJECTIVES, ENDPOINTS, AND ESTIMANDS

Table 4: Study ARGX-113-2010 Objectives and Endpoints

Objectives	Endpoints
Primary	
To assess the long-term safety and tolerability of treatment with efgartigimod PH20 SC in participants with BP	
 • Incidence and severity of treatment-emergent AEs, SAEs, and AESIs • Rate of treatment discontinuation because of safety concerns
Secondary	
To assess the long-term efficacy and durability of response with efgartigimod PH20 SC treatment in participants with BP	
 • Proportions of participants achieving^a: 
 – CR while off OCS for ≥ 8 weeks – CR or PR while off OCS for ≥ 8 weeks – CR while on minimal OCS therapy for ≥ 8 weeks. (Minimal OCS therapy is defined as ≤ 0.10 mg/kg/day of prednisone [or an equivalent dose of another OCS]) – CR while off both OCS and efgartigimod PH20 SC for ≥ 8 weeks^b – CR or PR while off both OCS and efgartigimod PH20 SC for ≥ 8 weeks^b • Duration of sustained remission • Proportion of participants who relapse • Time to relapse • Incidence and severity of relapse • BPDAI activity scores, IGA-BP scores, and itch NRS over time • Rate of treatment failure
Additional secondary	
To evaluate the impact of efgartigimod PH20 SC treatment in reducing long-term glucocorticoid-associated toxicity in participants with BP	GTI-related scores, including the GTI-AIS, GTI-CWS, and GTI-SL over time
To evaluate the impact of efgartigimod PH20 SC treatment on QoL in participants with BP	EQ-5D-5L, DLQI, and ABQoL scores over time
To evaluate the PD and immunogenicity of efgartigimod PH20 SC in participants with BP	
 • Percent change from baseline over time for anti-BP180 and anti-BP230 antibody levels • Incidence and prevalence of ADA against efgartigimod (serum levels)

Objectives	Endpoints
Exploratory	
████████████████████ ████████████████████	██ ████████

^a These endpoint criteria can only be met when participants are off rescue therapy.

^b The endpoint applies only to participants who have stopped receiving efgartigimod PH20 SC before protocol amendment 2 is effective.

No estimands have been defined for this OLE study.

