In addition, for all pharmacodynamic endpoints, descriptive statistics of the actual values and percent changes from baseline will also include GM and GSD. GM and GSD of percent changes from baseline are calculated as $100X \{ \exp(\theta) - 1 \}$ where θ is respectively the arithmetic mean and arithmetic SD of a variable calculated as $\log(\text{aval}) - \log(\text{base})$. GM and GSD are not applicable for descriptive statistics of the absolute changes from baseline.

4.2.3 *Presentation of results*

The SAF analysis set will be used for the PD evaluation. For tables by analysis visit, only the TPnB and last assessment analysis visits in a treatment period will be shown. Results for treatment period 2 will only be presented if at least 10 participants have a post-TP2B PD assessment.

All pharmacodynamic endpoints will be summarized by means of descriptive statistics at each analysis visit of interest in a treatment period. Actual values, changes from TPnB and percent changes from TPnB will be tabulated. Descriptive statistics of the actual values and percent changes from TPnB will also include GM and GSD. GM and GSD are not applicable for descriptive statistics of the absolute changes from TPnB.

	Statistical Analysis Plan	
ARGX-113-2010	Final analysis	Final 1.0 of 29APR2025

Listings will be created for [REDACTED] and anti-BP antibodies results over time, based on the ROL analysis set. Listings will always show the non-imputed results.

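### Disease-score, quality-of-life and anti-BP antibody endpoints are defined over time, but the SAP tabulates only baseline and one undated last value, so their course is not summarised

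*SAP*

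**What the plan says.** Protocol section 3 (Table 4) lists as secondary endpoints "BPDAI activity scores, IGA-BP scores, and itch NRS over time" and "Percent change from baseline over time for anti-BP180 and anti-BP230 antibody levels". SAP 1.1 (Table 1) repeats these and adds "EQ-5D-5L, DLQI, and ABQOL scores over time". The disease scores serve the objective "To assess the long-term efficacy and durability of response with efgartigimod PH20 SC treatment in participants with BP".

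SAP 2.2.4 (Table 3) derives a full set of analysis visits: every 4 weeks on IMP, every 8 weeks in observation or off IMP, and two follow-up visits.

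The presentation rules then cut this down:

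- Efficacy and quality of life (SAP 4.1.3): "For tables by analysis visit, only the study baseline and last assessment analysis visits will be shown", followed by "Other analysis visits will be included in listings".
- Antibodies (SAP 4.2.3): "For tables by analysis visit, only the TPnB and last assessment analysis visits in a treatment period will be shown". Period 2 appears only if at least 10 participants have a PD assessment after the period 2 baseline.
- Last assessment (SAP 2.2.6): the last nonmissing postbaseline value, at no set time. For PD it is taken per treatment period, and follow-up values are eligible.

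SAP section 8 still titles the corresponding tables as being over time. It lists tables and listings, but no figures.

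**The concern.** A baseline value and one last value give two points, the second at a different time for each participant. They cannot show when a score or antibody level changed, whether the change was held, or whether it was lost and regained.

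The last value is also often not an on-treatment value. BPDAI, IGA-BP, itch and the antibodies are measured at both follow-up visits, after dosing has ended. A reader of the tables could take the last-assessment row as the result on long-term treatment, when for most completers it would describe the off-drug follow-up. Participants who left early enter the same row at whatever time they were last measured.

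The protocol's own over-time endpoints would then reach the study report only through participant listings, which give no mean, distribution or n per visit.

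**Working it through.** The plan states no figure to reproduce, and "No formal hypothesis testing will be conducted in this open-label study", so no error rate or sample size is involved. The check is a count from the schedules of activities (protocol section 1.3, Tables 1 and 2), set against the presentation rules.

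**BPDAI, IGA-BP and itch NRS, on IMP from baseline (Table 2)**

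- Scheduled to week 48: weeks 2, 4, 8, 12, 16, 20, 24, 28, 32, 36, 40, 44, 48 = 13.
- Follow-up: EoTP + 4 weeks and EoTP + 8 weeks = 2.
- Total 13 + 2 = 15. Summarised: 1 (1/15 = 7%). Listed only: 15 − 1 = 14.

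The antibodies have the same 15 time points, with one last value summarised per treatment period. With a single treatment period that is again 1 of 15.

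**BPDAI, IGA-BP and itch NRS, in observation throughout (Table 1)**

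- Weeks 2, 4, 8, 16, 24, 32, 40, 48 = 8, plus EoTP + 8 weeks = 9.
- Summarised: 1. Listed only: 9 − 1 = 8.

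**Quality of life (EQ-5D-5L, DLQI, ABQOL)**

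- On IMP: week 8, then every 16 weeks (24, 40), and week 48 = 4. Summarised: 1.
- In observation: weeks 24 and 48 = 2. Summarised: 1.

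**Timing of the last value for a completer on drug**

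- Last permitted dose: week 48 (protocol Table 2, footnote l). Last scheduled BPDAI, IGA-BP, itch and antibody assessment: week 48 + 8 = week 56.
- Gap: 56 − 48 = 8 weeks off drug, give or take the visit windows.
- Quality of life is not scheduled in follow-up, so its last value for a completer is normally week 48. There the gap is the time course only.

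**Is the course summarised elsewhere?** SAP section 8 has no figure and no other by-visit table for these measures. By-visit tables are kept for ADA and NAb (SAP 4.3.3), so the format is already in use in this SAP.

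**The case against.** The best defence is that this is a deliberate and harmless choice. The study is descriptive, protocol 9.3.1 promises descriptive summaries without requiring them by visit, and baseline plus last is also the SAP's rule for laboratory, vital-sign and ECG tables. Nothing is discarded: intermediate values appear in listings 16.2.6.4 to 16.2.6.6, 16.2.6.9 to 16.2.6.11 and 16.2.6.13. All of that is correct, and it limits the point to reporting. It does not answer it, because these endpoints are worded as over time and listings do not summarise them.

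Three stronger readings are tempting, and the documents do not support them.

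- *That no table addresses durability.* Tables 14.2.1.1 to 14.2.1.9 cover remission held for at least 8 weeks, duration of sustained remission, relapse, time to relapse and relapse severity. Sustained remission is confined to those in complete remission off both OCS and IMP, and entrants under protocol versions 3 and 4 are non-evaluable. Relapse and time to relapse, however, cover anyone with CDA, CR or PR in the rollover set.
- *That a participant who flares for months and recovers looks the same as a stable one.* After disease control, a long flare would ordinarily meet the protocol's relapse definition and be counted. If it is the first relapse, its severity is also tabulated as a BPDAI difference. What goes unsummarised is recovery, later relapses and changes short of relapse.
- *That by-visit tables would reveal the early response of former placebo participants.* SAP 2.1.2 pools the prior arms, so they would not.

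The relapse and remission tables still do not fill the gap. They rest on investigator-reported status, take only the first relapse or evaluation, and say nothing about the course of itch, quality of life or antibodies.

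**Conclusion.** The point holds as a reporting gap. Endpoints defined over time are tabulated at baseline and at one last value of no fixed date. Of the scheduled postbaseline assessments, 1 of 15 (on IMP from baseline) or 1 of 9 (observation) is summarised for BPDAI, IGA-BP and itch, 1 of 4 or 1 of 2 for quality of life, and one per treatment period for antibodies. For completers on drug, the one BPDAI, IGA-BP, itch or antibody value is normally about 8 weeks off drug, so no row gives an on-treatment level.

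The counts assume that the scheduled visits are attended, with no unscheduled or early discontinuation visits. The timing statement assumes a nonmissing value at EoTP + 8 weeks and, for antibodies, applies to the participant's final treatment period. No listed table's estimate or denominator is wrong because of this. Durability by disease status has its own tables and is not part of the finding.

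**What to change.** In SAP 4.1.3 and 4.2.3, replace the restriction with a rule along these lines: tables present baseline (TPnB for PD) and every Table 3 analysis visit at which the parameter is scheduled, in separate blocks labelled by phase, period and subperiod (observation, On IMP, Off IMP, follow-up), with n per visit; the last assessment is kept as an additional row.

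The block labels are needed because Table 3 counts weeks from the start of each subperiod. Week 8, for example, occurs in the observation phase and in each On IMP and Off IMP subperiod, with different origins. Pooling them would mix on-drug and off-drug values. Keep the existing condition of at least 10 participants for PD treatment period 2. The Table 3 windows and selection rules need no change.

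The visits are already derived for the listings, so the cost is longer tables. Some late visits and small subperiods will have few participants. Because missing values are not imputed (SAP 2.3.1), the later rows describe those still under assessment. The n per visit makes this visible but does not correct for it.
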